### 13.4 Patient Accrual

All patients enrolled on ACCL0933 will be offered the chance to participate in the anti-fungal screening study. We anticipate that at least 80% of the patients in the parent trial will enroll in this ancillary study resulting in an estimated 440 patients at baseline. Those who consent will undergo Platelia *Aspergillus* EIA and Fungitell Assay testing. Blood sampling will be conducted twice weekly during anti-fungal prophylaxis treatment after each course of chemotherapy.

Each patient will have the potential for multiple courses of chemotherapy with each course having variable durations of neutropenia. Based on data from the AAML0531 trial, we have estimated the number of patients progressing from the first course of chemotherapy through the fourth course of therapy as well as duration of neutropenia for each course (see Table 2). Given a planned frequency of biomarker testing of twice per week, estimates of the number of Platelia *Aspergillus* EIA and Fungitell Assays performed during each chemotherapy course are provided (see Table 2).

**Table 2.** Estimated number of Platelia *Aspergillus* EIA and Fungitell Assay performed per course.

Chemotherapy course	Estimated Duration of neutropenia* (days)	# of testing time points for 1 patient during neutropenia †	Platelia EIA	Fungitell Assay
I (n=440)	20	6	2640	2640
II (n=380)	18	5	1900	1900
III (n=337)	17	5	1685	1685
IV (n=216)	28	8	1728	1728
Total	-	-	7953	7953

\*Based on median duration of neutropenia for each course from AAML0531 trial

†Based on a plan for 2 tests per week during neutropenic period

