#### 4.1.2 Empirical Antifungal Therapy

The persistence of fever for 5 days despite broad spectrum antibiotic therapy warrants the investigation of IFI and initiation of empiric antifungal therapy. Amphotericin B (lipid products) or voriconazole are recommended options based on their broad spectrum of antifungal activity. Assigned antifungal prophylaxis should be held during administration of these other systemic antifungal agents.

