**7.0 EVALUATIONS/MATERIAL AND DATA TO BE ACCESSIONED**

Timing of protocol therapy administration, response assessment studies, and surgical interventions are based on schedules derived from the experimental design or on established standards of care. Minor unavoidable departures (up to 72 hours) from protocol directed therapy and/or disease evaluations (and up to 1 week for surgery) for valid clinical, patient and family logistical, or facility, procedure and/or anesthesia scheduling issues are acceptable per COG administrative Policy 5.14 (except where explicitly prohibited within the protocol).

All baseline studies must be performed prior to starting protocol therapy unless otherwise indicated below.

**7.1 Required and Optional Clinical, Laboratory and Disease Evaluations  
Obtain prior to start of phase unless otherwise indicated.**

STUDIES TO BE OBTAINED	Baseline	Course 1 #	Subsequent Courses #	End of ACCL0933 Therapy
REQUIRED				
History	X			
Physical Exam (Ht, Wt, BSA)	X			
CBC, differential, platelets	X	X	X	X
Creatinine, SGPT, SGOT, bilirubin	X	X	X	X
IFI checklist		X*	X*	X*
OPTIONAL				
Sample for SNP Genotyping		X %		
GM, BG Assays		2x weekly @	2x weekly @	

# Course 1 of fluconazole or caspofungin follows Course 1 of AML therapy. *Subsequent Courses* refers to protocol-directed antifungal prophylaxis, not AML therapy.

\* Submit relevant IFI checklist documents via the Document Imaging System: [contact] at the end of each course of protocol therapy. See Section 10.2 for further details.

% Obtain at end of Course 1, optimally when the patient has ANC > 1000/ $\mu$ L and no circulating blasts.

@ Collect specimens twice weekly during the period of neutropenia (until ANC > 100-500/ $\mu$ L). See Section 13.1 for specimen collection details. It is suggested that specimens be obtained on Mondays and Thursdays but other days are acceptable if more convenient. A minimum of 2 days should separate each specimen collection. All specimens must be collected in the specimen vials provided by MiraVista Laboratories in the shipped lab collection kits. Alternative specimen vials should never be used as they may contribute to false results.

**This table only includes evaluations necessary to answer the primary and secondary aims. Obtain other studies as indicated for good clinical care.**

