### 8.3 Discontinuation from IFI Observation Criteria

**Patients who are taken off protocol therapy (but are not off study) must be followed for all infection endpoints until they meet the Discontinuation from IFI Observation Criteria (below) or until they meet the Off Study Criteria (See Section 8.2).**

- a) Begin conditioning for HSCT.
- b) Begin a new chemotherapy regimen for AML that is refractory to, or relapsed with current AML chemotherapy.
- c) Two weeks after recovery from neutropenia following completion of the final planned AML chemotherapy course.

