##### 13.1.2 Sample Collection

Whole blood samples will be collected twice weekly during the period of neutropenia (until ANC > 100-500/ $\mu$ L). It is suggested that specimens be obtained on Mondays and Thursdays but other days are acceptable if more convenient. A minimum of 2 days should separate each specimen collection.

In order to perform both assays on a single specimen (Platelia™ Aspergillus EIA and Fungitell® beta-D glucan assay), collect 5 mL of whole blood in a gold top serum-separator tube (provided by MiraVista) and label with the site number, COG ID number, and date (labels will be provided with the sample shipping kit). Although the above volume of blood testing will likely represent a small fraction of the blood testing performed during the period of 1 week, it may result in an important increase in certain patients (i.e., smaller children or anemic children). Therefore, we have set the following maximum limits per kilogram for blood draws related to this ancillary study: 3 mL of blood/kg body weight in an 8 week period.

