#### 13.8.2 Sensitivity, Specificity, PPV, and NPV

The validity of a biomarker is based on whether the study appropriately categorizes patients with and without the illness in question (sensitivity and specificity). Alternatively the validity of a test can be measured by how well the test results predict the presence or absence of the disease (PPV and NPV). Collectively, sensitivity, specificity, PPV, and NPV are often referred to as the test's operating characteristics with the sensitivity and NPV being the most clinically relevant parameters for this study. Each component of the operating characteristics will be calculated based first on the entire cohort. As indicated in the sample size estimates above the incidence of IFI will vary between the two study arms. It is well documented that variations in the incidence/prevalence of a disease will impact the operating characteristics of a diagnostic test specifically for the PPV and NPV. Therefore, each assay's sensitivity, specificity, PPV and NPV will also be calculated separately for each study arm.

The operating characteristics for both the Platelia *Aspergillus* EIA and the Fungitell Assay will be computed at the patient level for each of the sub-aims as follows:

- a) Outcome of IA only **or** all IFI defined as a single positive test for either the Platelia *Aspergillus* EIA **or** the Fungitell Assay as compared to the EORTC/MSG criteria for proven or probable IA only **or** all IFI.
- b) Outcome of IA only defined as a single positive test for Platelia *Aspergillus* EIA only as compared to the EORTC/MSG criteria for proven or probable IA only.
- c) Outcome of all IFI defined as a single positive test for the Fungitell Assay as compared to the EORTC/MSG criteria for all proven or probable IFI.

Sensitivity, specificity, PPV and NPV and their accompanying 95% confidence intervals will be calculated using STATA statistical software version 11.0 (College Station, TX). As noted above, these parameters will first be calculated for the entire cohort and then for each study arm separately. The latter analyses are important as the incidence of IFI may vary by study arm thus impacting the interpretation of the assay results. A patient with multiple episodes of IFI will only be included in the analyses as a single IFI.

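### Section 13.4 ties biomarker sampling to prophylaxis while other sections tie it to neutropenia, and Section 13.8.2 sets no test-to-IFI window, so an IFI in unsampled time can be scored as an assay miss

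*Combined protocol and SAP*

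**What the plan says.** **Sampling.** Section 13.4 states: "Blood sampling will be conducted twice weekly during anti-fungal prophylaxis treatment after each course of chemotherapy". Table 2 in the same section derives the number of tests from the median duration of neutropenia in each course, and its footnote reads "Based on a plan for 2 tests per week during neutropenic period". Section 13.1.2, the collection instruction, says "Whole blood samples will be collected twice weekly during the period of neutropenia", up to an ANC threshold. Section 7.2.1 agrees. In the Section 7.1 table, the footnote on the assay row also agrees: "Collect specimens twice weekly during the period of neutropenia". However, the column for later courses in that table "refers to protocol-directed antifungal prophylaxis, not AML therapy", and the end-of-therapy column has no assay entry. The delivery maps (Sections 4.2.1 and 4.3.1) place the assays on the prophylaxis calendar and refer to Section 13 for details.

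**Prophylaxis.** It normally runs to the same ANC threshold. If empiric therapy starts, Section 4.1.2 says "Assigned antifungal prophylaxis should be held during administration of these other systemic antifungal agents"; Section 4.1 has the same rule, with resumption if the other agent stops before ANC recovery. Section 8.1 also ends protocol therapy on refusal or by physician decision.

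**Follow-up.** Under Section 8.3, patients off protocol therapy but still on study "must be followed for all infection endpoints until they meet the Discontinuation from IFI Observation Criteria". The latest of these points is two weeks after neutrophil recovery from the final planned course.

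**Analysis.** Section 13.8.2 says the operating characteristics "will be computed at the patient level for each of the sub-aims as follows", with one positive test sufficing. It states no interval between test and IFI and no exclusion for unsampled time. Section 13.3 hypothesises sensitivity above 90% for each assay.

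**The concern.** The two sampling rules coincide in the ordinary course, because prophylaxis and sampling share an ANC endpoint. They separate when prophylaxis is off during neutropenia. The main case is the hold for empiric therapy, which follows persistent fever and is a time when IFI is under suspicion. Others are a hold for liver dysfunction (Section 5.2), discharge without continued caspofungin (Section 4.1) and early removal (Section 8.1). A site that followed the Section 13.4 sentence could stop drawing samples at that point.

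A second gap remains whichever rule is followed. No text says whether a consenting patient off protocol therapy is still sampled in later neutropenic periods, and no rule requires samples in the two weeks after the final recovery. IFI observation runs through both.

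At stake is the estimated sensitivity, which Section 13.8.2 names, with negative predictive value (NPV), as most clinically relevant. An IFI that no sample could have detected would be charged to the assay. Serum not drawn cannot be recovered later.

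**Working it through.** **1. Reproduce Table 2.** Time points = days of neutropenia × 2/7, rounded.

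| Course | n | Days | Days × 2/7 | Time points | Tests |
|---|---|---|---|---|---|
| I | 440 | 20 | 5.71 | 6 | 2640 |
| II | 380 | 18 | 5.14 | 5 | 1900 |
| III | 337 | 17 | 4.86 | 5 | 1685 |
| IV | 216 | 28 | 8.00 | 8 | 1728 |

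The total is 7953 per assay, as printed. The budget therefore already assumes sampling throughout neutropenia. If sampling stopped whenever prophylaxis was off, and 5% to 30% of neutropenic days were off prophylaxis (assumed), 398 to 2386 of these tests would be lost (0.05 × 7953 to 0.30 × 7953).

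**2. Reproduce the expected events (Section 13.8.1).** Ancillary patients: 0.80 × 550 = 440, or 220 per arm. IFIs: 220 × 8% = 17.6 (18 in the plan) and 220 × 2% = 4.4 (4 in the plan), total 22. IA events: 6 plus 1 to 2, or 7 to 8.

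**3. Effect on sensitivity.** Let k be the number of IFIs with no informative sample and no earlier positive, and s the sensitivity among the rest. Observed sensitivity = s × (N − k)/N.

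| N | k | s = 1 | s = 0.90 |
|---|---|---|---|
| 22 IFI | 1 | 95.5% | 85.9% |
| 22 IFI | 2 | 90.9% | 81.8% |
| 22 IFI | 3 | 86.4% | 77.7% |
| 22 IFI | 4 | 81.8% | 73.6% |
| 7 IA | 1 | 85.7% | 77.1% |
| 8 IA | 1 | 87.5% | 78.8% |

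Even a perfect assay falls below 90% with three such IFIs among 22, or one among 7 or 8 IA events.

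**4. How likely is that?** The documents give no rate of holds or early removals, so the share u of IFIs with no informative sample is assumed, and events are treated as independent (binomial).

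| u | P(3 or more of 22) | P(1 or more of 7) | P(1 or more of 8) |
|---|---|---|---|
| 5% | 9% | 30% | 34% |
| 10% | 38% | 52% | 57% |
| 20% | 85% | 79% | 83% |

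**5. Effect on NPV.** Take 440 patients, 22 IFIs, 90% sensitivity and an assumed 90% specificity. True negatives = 0.90 × 418 = 376.2. With k = 0, false negatives = 2.2 and NPV = 376.2/378.4 = 99.4%. With k = 4, false negatives = 22 − 0.90 × 18 = 5.8 and NPV = 376.2/382.0 = 98.5%.

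**The case against.** The strongest reply is that the conflict is one descriptive sentence in a section on accrual. The collection instruction (13.1.2), the evaluation summary (7.2.1), the assay-row footnote in 7.1 and Table 2 all say neutropenia, and the delivery maps point to Section 13. A hold is not a removal: Section 8.1 keeps a patient on empiric therapy in the protocol for later courses. This largely stands. A reader might infer from the column definition that Section 7.1 is a prophylaxis rule; its assay footnote says otherwise. Nor do the documents show that sites will in fact sample differently, only that the text permits it.

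A reader might also infer that every IFI after sampling stops is counted as a miss. It is not. One earlier positive makes the patient a true positive, and the adult studies cited in Section 13.2.3.1 report positivity a median of 17 days (GM assay, proven IA) and of 10 and 5 days (Fungitell) before diagnosis. Only patients with no earlier positive are affected.

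Finally, the Section 13.3 hypotheses concern patients on prophylaxis, so IFIs off prophylaxis might be thought out of scope. But then they should be excluded from scoring, and Section 13.8.2 does not do so. An analysis rule is needed on either reading.

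**Conclusion.** The point holds in a limited form. The Section 13.4 sentence conflicts with the neutropenia rule stated elsewhere, sampling after protocol therapy ends is not addressed, and Section 13.8.2 does not confine scoring to sampled time. Together these allow an undetectable IFI to be scored as a false negative, which lowers estimated sensitivity. Because the hypotheses rest on about 22 IFIs and 7 to 8 IA events, three or one such cases respectively put the point estimate below 90% even for a perfect assay. The number affected is assumed throughout.

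Two stronger readings are not supported. A material loss of NPV does not follow: four such IFIs move it by about one percentage point under the stated assumptions. A known imbalance between arms does not follow either. Objective 1.2.3 asks whether caspofungin leads to less empiric therapy, so unequal loss is possible, and matters because Section 13.8.2 also reports by arm, but the documents do not establish it. This is a cheap improvement to an optional ancillary study and does not touch the primary comparison.

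**What to change.** 1. **Section 13.4:** replace the sentence with the Section 13.1.2 neutropenia rule. State there and in both delivery maps that sampling continues while prophylaxis is held. The assay footnote in Section 7.1 already states the neutropenia rule and needs no change to it.
2. **Off protocol therapy:** say whether consenting patients still under Section 8.3 observation are sampled in later neutropenic periods.
3. **Section 13.8.2:** prespecify a window around sampled time and score IFI status only within it. Apply it identically whatever the test results; dropping only test-negative patients would bias sensitivity upwards. IFIs in unsampled time, including the two weeks after final neutrophil recovery, are then not scored as false negatives. Report how many fall outside the window, by arm.

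**Cost:** a few sentences. Sampling during holds adds nothing to the 7953 tests per assay in Table 2. Sites may make a few more draws than under the Section 13.4 wording, within the Section 13.1.2 blood-volume cap. The window may leave fewer scored events and wider intervals. Clinical management is unaffected, because Section 13.1.8 withholds results from treating physicians.

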### 13.5 Gold Standards for IFI and IA Infections

The criteria established by the EORTC/MSG for proven or probable IFI and proven or probable IA will be used as the gold standard. These definitions have been used as the primary endpoints for prior studies validating Platelia *Aspergillus* EIA and the Fungitell Assay.

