### 13.1.8 Galactomannan and Beta-D glucan Assays

Testing will be performed by technicians blinded to each patient's clinical information. **Test results will not be made available to treating physicians since the utility of these tests is not yet established in children and because we will not be conducting testing in real time. Thus, results will not be utilized for clinical decision-making.**

To our knowledge BG testing is not routinely performed at many pediatric centers but may be performed at some of the COG sites while GM testing is currently performed at a number of pediatric centers. Regardless of the number of institutions offering such testing options, we anticipate that such testing will be ordered by a subset of treating physicians. The local BG and GM results will not be included in our final analysis of the 2 biomarker assays' operating characteristics. However, these results may effect a change from fungal prophylaxis to preemptive or empiric therapy and may encourage or discourage more comprehensive efforts to diagnose a proven or probable IFI in any given patient. This in turn may falsely influence our evaluation of the 2 biomarker assays' operating characteristics. For each patient we will identify whether local BG or GM testing has been performed and, via a sensitivity analysis, explore whether such a practice influences the operating characteristics. The plans for this sensitivity analysis are described in more detail in Section 13.8.4 below.

The Platelia *Aspergillus* EIA study is reported as a GM index. We will use the FDA-approved threshold of  $\geq 0.5$  GM index on a single test sample as our criteria for a positive test result. The Fungitell Assay is reported in pg per mL of patient's serum. The manufacturer recommendation for a single positive Fungitell assay result of  $\geq 80$  pg/mL will be used to define a positive test.

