##### 13.6.1.2 Justification for IFI Gold Standard

We have chosen to use EORTC/MSG defined proven or probable IA or IFI (Appendix II) as the gold standard. The ideal gold standard to compare to each biomarker would be a positive culture of a fungal organism from blood or infected tissue. However, there are significant challenges to establish the presence of fungal infection with isolation of the etiologic organism. Certain molds such as *Aspergillus*

do not grow routinely in blood cultures, the ability to obtain tissue for culture can be impacted by the size and location of a visceral lesion, and the clinical status of a patient may preclude invasive procedures to obtain cultures. Therefore, an alternate endpoint to identify all patients who truly have IFI is necessary. This issue has been addressed by the EORTC/MSG. This group of experts initially created criteria based on clinical, radiographic and culture data to define possible, probable and proven IFI in 2002 and revised these criteria in 2009. These criteria have served as the primary endpoint for major trials of antifungal drug efficacy, in strategy trials, for formulating clinical practice guidelines, as well as for undertaking epidemiologic studies. Consistent use of these criteria as the primary endpoint will allow for comparison of the resultant data to prior and future studies.

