#### 13.8.4 Sensitivity Analysis

Sensitivity analyses will be explored for reasoning expressed in both Sections 13.1 and 13.7 above. The first sensitivity analysis will attempt to identify the direction and magnitude of the bias resulting from the availability of clinical BG and GM testing outside of the ancillary study. Such testing has the potential to change the treating clinician's approach for diagnosing an IFI. It is possible that these test results could result in more or less investigation (i.e., radiologic imaging) to identify an IFI which could ultimately impact on the incidence of identified IFI. Therefore, in addition to calculating the operating characteristics for all patients enrolled as described in Section 13.8.2 above, the same operating characteristics will be calculated after excluding all patients that had at least 1 biomarker test result available to the treating clinician.

The second sensitivity analysis will be performed to explore the impact of the various factors described in Section 13.7 that may contribute to a positive result for either biomarker. False positive results would impact the final interpretation of sensitivity and PPV for each of the assays. However, it is also possible that one of the factors listed in Table 3 is present in a patient that truly has an IFI. Therefore, we plan to still include all patients in the primary analysis for calculation of each assays' operating characteristics. In this sensitivity analysis, we will eliminate all patients with a positive test that correlates in time with at least 1 of the factors listed in Table 3.

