#### Indirect tests (detection of antigen or cell-wall constituents)e

- Aspergillosis
  - Galactomannan antigen detected in plasma, serum, bronchoalveolar lavage fluid, or CSF
- Invasive fungal disease other than cryptococcosis and zygomycoses
  - $\beta$ -D-glucan detected in serum

---

**NOTE.** Probable IFD requires the presence of a host factor, a clinical criterion, and a mycological criterion. Cases that meet the criteria for a host factor and a clinical criterion but for which mycological criteria are absent are considered possible IFD.

a Host factors are not synonymous with risk factors and are characteristics by which individuals predisposed to invasive fungal diseases can be recognized. They are intended primarily to apply to patients given treatment for malignant disease and to recipients of allogeneic hematopoietic stem cell and solid-organ transplants. These host factors are also applicable to patients who receive corticosteroids and other T cell suppressants as well as to patients with primary immunodeficiencies.

b Must be consistent with the mycological findings, if any, and must be temporally related to current episode.

c Every reasonable attempt should be made to exclude an alternative etiology.

d The presence of signs and symptoms consistent with sepsis syndrome indicates acute disseminated disease, whereas their absence denotes chronic disseminated disease.

e These tests are primarily applicable to aspergillosis and candidiasis and are not useful in diagnosing infections due to *Cryptococcus* species or *Zygomycetes* (e.g., *Rhizopus*, *Mucor*, or *Absidia* species). Detection of nucleic acid is not included, because there are as yet no validated or standardized methods.

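### Galactomannan and beta-D glucan are scored against a case definition that can itself rest on those tests, and the plan does not say whether the review committee uses them

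*Combined protocol and SAP*

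**What the plan says.** Section 13.5 sets the reference standard: "The criteria established by the EORTC/MSG for proven or probable IFI and proven or probable IA will be used as the gold standard". Section 13.6.1.2 ties it to the printed text: "We have chosen to use EORTC/MSG defined proven or probable IA or IFI (Appendix II) as the gold standard".

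In Appendix II the indirect mycological tests are, for aspergillosis, "Galactomannan antigen detected in plasma, serum, bronchoalveolar lavage fluid, or CSF", and, for invasive fungal disease other than cryptococcosis and zygomycosis, beta-"D-glucan detected in serum". The note there says "Probable IFD requires the presence of a host factor, a clinical criterion, and a mycological criterion". A case with host and clinical criteria but no mycological criterion is only possible, and so falls outside the standard.

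Section 13.1.8 expects some treating physicians to order GM or BG locally. Of the study assays it says "Test results will not be made available to treating physicians". Of the local ones it says "The local BG and GM results will not be included in our final analysis of the 2 biomarker assays".

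Sections 9.3.2, 10.2 and 13.6 list what the committee receives. Under non-culture mycology each list, introduced by *i.e.*, names only Histoplasma and cryptococcal antigens. The committee's stated blinding is to antifungal exposure or treatment assignment.

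Section 13.8.4 adds a sensitivity analysis, run beside the all-patient analysis, in which the operating characteristics are recalculated "after excluding all patients that had at least 1 biomarker test result available to the treating clinician".

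**The concern.** When an index test can supply part of the reference standard, the comparison is partly circular (incorporation bias). A patient with prolonged neutropenia and a suggestive CT is a possible case. A positive local GM makes that patient probable, and the study GM, which measures the same analyte, is then credited with detecting the case. Had the GM been negative, the patient would have stayed outside the standard and could not have counted as a miss. Sensitivity rises because misses are never enrolled as cases. PPV rises because would-be false positives become true positives.

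The route is open in this population. Section 13.4 expects median neutropenia of 17 to 28 days per course, against a host criterion of more than 10 days. Sections 13.2.2 and 13.6.1.2 say that moulds seldom grow in blood culture and that tissue is often unobtainable. Antigen may therefore be the deciding evidence in some probable aspergillosis cases.

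At stake is whether the hypotheses of over 90% sensitivity in Section 13.3 are judged fairly. These results are meant to inform later use of the assays to guide treatment.

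**Working it through.** **The plan's case counts (Section 13.8.1).** Cohort: 0.80 × 550 = 440, or 220 per arm. IFI: 220 × 0.08 = 17.6 (stated 18) and 220 × 0.02 = 4.4 (stated 4), 22 in all. Aspergillosis (IA) at one third: 18/3 = 6 and 4/3 = 1.3 (stated 1 to 2), so 7 to 8 in all. The counts reproduce. Section 13.8.2 analyses the entire cohort first and scores GM alone against IA only. The relevant denominators are therefore 22 IFI and 7 to 8 IA.

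**Size of the bias, first model.** Assumptions, none of them in the documents: sensitivity is 75% in cases defined without antigen and 100% in the k cases defined by antigen. Apparent sensitivity = [0.75 × (n − k) + k] / n.

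- n = 22, k = 2: 17.0/22 = 77%
- n = 22, k = 4: 17.5/22 = 80%
- n = 22, k = 6: 18.0/22 = 82%
- n = 7, k = 2: 5.75/7 = 82%
- n = 7, k = 4: 6.25/7 = 89%

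The excess is about 2 to 7 points for all IFI and 7 to 14 points for IA. On the Section 13.8.1 split, k = 6 of 22 is near the upper end. Yeast in blood culture is already proven disease, and the disseminated candidiasis criterion itself requires candidemia, so antigen-dependent cases should be mostly mould.

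**Size of the bias, second model.** Let s be true sensitivity, f the share of true cases confirmable without antigen, and t the share of the rest tested locally. Assume that local and study assays agree and that s is the same in both groups. Apparent sensitivity = [f·s + (1 − f)·t·s] / [f + (1 − f)·t·s].

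- s = 0.70, f = 0.5: (0.35 + 0.175)/(0.5 + 0.175) = 77.8% at t = 0.5; 82.4% at t = 1
- s = 0.70, f = 0.2: 87.5% at t = 0.5; 92.1% at t = 1
- t = 0, or an antigen-free standard: 70%

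**What the Section 13.8.4 exclusion costs.** The share of cases tested locally is not given, so it is varied here. If every remaining case is detected, the exact two-sided 95% lower limit is 0.025^(1/n).

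- No case dropped: 22/22, lower limit 84.6%
- 10% of cases tested: about 20 IFI remain; 20/20, 83.2%
- 50% tested: 11 IFI (about 3.7 IA) remain; 11/11, 71.5%
- 80% tested: about 4.4 IFI (1.5 IA) remain; 4/4, 39.8%

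Prevalence moves too. It is 22/440 = 5.0% at the start. With 30% of the 418 non-cases tested, 293 non-cases remain, and prevalence is 3.6% if 50% of cases are tested and 1.5% if 80% are. If only 10% of cases are tested it rises to 6.3%. The direction of the shift in PPV and NPV thus depends on an input that the plan does not give.

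**The case against.** The strongest reply is that no antigen-defined case may ever arise. Read literally, the lists in Sections 9.3.2, 10.2 and 13.6 mean that the committee never receives local GM or BG. Study assays are batched and withheld from clinicians. Local results are kept out of the assay analysis.

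This stands in part: a reader might infer that the accuracy figures are certain to be inflated, and the documents do not support that. But the reply does not close the gap. If the lists are exhaustive, Appendix II is not being applied as printed; if they are not, the standard is circular. The sentence on local results concerns assay data, not case classification, and no text withholds study results from the committee.

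A reader might also take Section 13.8.4 as the plan's failed remedy for circularity. It is not offered as one. It is a supplementary analysis aimed at clinicians who change their work-up after seeing a local result. It does also remove locally antigen-defined cases, because a patient without a local result cannot become probable through one.

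Nor do the documents show that the excluded patients are those in whom infection was suspected. Physician-ordered testing makes that likely, but local surveillance is compatible with the text, and no rate or indication is stated.

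The reply that EORTC/MSG gives comparability with earlier studies is sound. It is a reason to report that standard as well, not to report it alone.

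**Conclusion.** The point holds as a gap in the plan with a conditional bias. The Section 13 standard, as printed, admits the two tests under evaluation; nothing removes them or blinds the committee to them; and the committee's data lists conflict with the unmodified criteria. If antigen evidence is used, sensitivity and PPV are biased upward by the amounts worked out above. Those amounts rest on assumed sensitivities, assumed agreement between local and study assays, and an assumed number of antigen-defined cases. Proven cases, and probable cases with culture, cytology or microscopy, are unaffected.

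A larger effect can be had by using only the 18 fluconazole-arm infections, but the first planned analysis covers both arms, and GM alone is scored against IA only.

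The exclusion analysis is not a substitute for an antigen-free standard. It removes locally antigen-defined cases only by dropping every locally tested patient, including proven and culture-based cases, and probably does so selectively. It also gives no protection if study results reach the committee.

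The point concerns the optional assay study; no effect on the primary treatment comparison is claimed. The change should be made, since it is cheap and can be specified before cases are classified.

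**What to change.** - State whether local and study GM/BG results go to the committee and may be used in classification, and reconcile Sections 9.3.2, 10.2 and 13.6 with Appendix II.
- For Section 13, have the committee also classify each case without GM/BG evidence and blind to all GM/BG results: proven, or probable on culture, cytology or microscopy. Record this before any antigen result is shown.
- Report the operating characteristics in all consenting patients against this antigen-free standard, preferably as the main reference, beside the full EORTC/MSG standard for comparability.
- Keep the full criteria for the clinical endpoints, and keep the Section 13.8.4 exclusion as already planned.

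The cost is one extra field on the committee form, a classification step and some SAP wording. There are two statistical costs. Reference events become somewhat fewer, in a set of only about 22 IFI. True cases supported by antigen alone count as non-cases, so study positives in them become false positives and apparent specificity and PPV fall. The antigen-free standard therefore errs in the other direction, which is why both sets of results should be shown.
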